### **7.2.10 Telephone Assessments**

Telephone assessment will be performed at **week 16** and **week 24**. During these calls participant compliance and adverse event information will be collected. At the week 24 assessment participants will be reminded to stop taking the study drug. Participants will also be reminded to bring in any remaining drug to their final study visit.

### **7.2.11 Genetic blood sample**

Blood samples can be collected from participants who consent to the optional genetic sub-study. Preferably this will be collected at baseline at the same time blood is collected for biochemistry, but can be done at any point after genetic sub-study consent up until the end of the study.

9ml of blood should be taken from consenting patients and collected in EDTA tubes. No processing is required but samples should be mixed well and frozen on the day of collection. These will be marked with the patient's trial number, initials and date of birth. Samples should be stored at -80°C until shipment. If sites are unable to store samples at -80°C then samples can be stored at -20°C but must be shipped within 6 months of collection

The trial manager for the study should be notified when samples are ready to send. The trial manager will then provide a contact name and delivery address where the samples should be dispatched.

Samples should be sent in batches of approximately 50 samples and should be shipped frozen on dry ice by courier.

Full details for processing and shipment of genetic samples will be provided in the ISF.

### **7.2.12 Blood serum biomarker sample**

At baseline participants will provide a baseline safety blood sample. At the same time blood serum samples will be collected for biomarkers of bone metabolism. They will also be collected at week 26.

7ml of blood should be collected in plain blood tubes (no gel or anticoagulant), spun and the serum should be stored in 2-3 x 1ml aliquots. Samples should be frozen at -70°C or below until ready for shipment for central analysis. Full details for processing and shipment of serum biomarker samples will be provided in the ISF.

**Table 7–1: Schedule of Assessments**

	Baseline a	Post-randomisation	Week 2	Week 4	Week 6	Week 8	Week 16	Week 24	Week 26
Informed Consent	X								
Demographics b	X								
Inclusion/Exclusion Criteria	X								
Relevant medical history/current medical conditions	X								
Biochemistry c	X								
Blood serum for biomarkers of bone metabolism	X								X
X-Rays d	X e		X	X	X	X			X
NRS Scoring	X		X	X	X	X			X
Analgesia usage	X		X	X	X	X			X
DASH Questionnaire	X		X	X	X	X			X
Urine pregnancy test f	X								
Pill count				X		X			X
CRPS-I assessment					X				X
Active range of movement						X			X
Grip strength assessment						X			X
Study drug administration g		X h →							
Concomitant medication	X →								
Adverse Events i		X →							
Optional genetic sub-study blood sample j	X →								
Telephone Assessment k							X	X	

### Notes for Table 7–1

---

- a All baseline assessments must be completed in time to allow a participant to commence study therapy within 14 days of their initial fracture.
- b Demographic information includes: age, gender, menopausal status, smoking history and alcohol consumption.
- c Minimum biochemistry requirement includes: creatinine, albumin, calcium and corrected/adjusted calcium.
- d X-rays must be performed +/- 2 days from scheduled visit date, except if it ties in with routine follow up/research clinic or at Week 26 X-ray where it can be +/- 7 days.
- e This X-ray refers to X-ray at time of fracture.
- f For women of childbearing potential
- g Discontinuation of study drug does not constitute withdrawal from trial. Unless there is another reason participants should continue to be followed up as per protocol.
- h Study drug administration must commence within the 14 days following initial trauma or within the 7 days following randomisation, whichever comes first.
- i Adverse events should be documented from date of randomisation to last study visit. Any adverse events ongoing at last study visit should be followed up until resolution or no longer medically indicated.
- j The optional genetic blood sample (9ml in EDTA tube) can be taken any time during the study. The participant must have given separate consent for this.
- k Telephone assessment will include questions about drug compliance and adverse event information. At week 24 patients will be reminded to stop taking study drug and bring all medication with them to their final study visit (week 26).

## 8. DATA COLLECTION

Data will be collected from baseline to the last study visit. Data will be entered on CRFs and should be completed in accordance with the CRF completion guidelines issued for the study. All CRFs must be returned to the ECTU for data entry and ultimately, statistical analysis.

CRFs for the study will be returned and stored in line with current regulatory requirements. Other essential documents, including source data, consent forms, and regulatory documents, will be archived by or for the Investigator in an appropriate archive facility in line with current regulatory requirements and made available for monitoring, audit and regulatory inspection.

## 9. STATISTICS AND DATA ANALYSIS

### 9.1 SAMPLE SIZE CALCULATION

The proposed sample size is 250 per arm (500 in total, not including post-randomisation exclusions). The study is powered to detect a 15% difference in the proportion of patients who have evidence of fracture healing on the week 4 radiograph since this is considered to be a clinically significant difference. A total sample size of 500 patients gives at least 90% power at the 5% significance level (2-sided) to detect an absolute difference of 15% in the 4 week radiological healing rates. This holds irrespective of the actual rate in the control group. Even if the rate of non-compliance is as high as 20% then there will still be over 80% power to detect the same 15% difference in 4 week radiological healing rates in a per-protocol analysis of compliant patients.

The sample size calculation given above is based on a conventional superiority comparison. The primary question being addressed in the trial can be viewed as a non-inferiority comparison, and so the implications of using the proposed sample for a non-inferiority analysis was also explored. In a recent study, funded by the Chief Scientist's Office of the Scottish Government which investigated the effects of vitamin C and placebo on wrist fracture healing, it was found that the average time to radiological healing in undisplaced wrist fractures was 42 days (SD 13) and in displaced fractures 48 days (SD 13). ([name], unpublished data). From a clinical point of view we feel that a 10% non-inferiority margin in time to radiological healing (i.e. less than 4 days) would not be clinically significant. Conversely, if the intervention delayed healing by more than 10% this would be clinically significant given that resolution of symptoms such as pain and restoration of function correlate closely with fracture healing. As is apparent from Table 9–1, the current sample size provides good power to demonstrate non-inferiority with a 10% margin if the true mean delay in healing is up to one day, and reasonable power for a true mean delay of up to 2 days. With the more stringent 7.5% margin there is good power to demonstrate non-inferiority if the treatments are equivalent, and reasonable power for a true mean delay of up to one day. Another way to look at this same issue is to note that with the planned sample size the resulting 95% confidence interval for the mean delay in healing will be the observed mean difference plus/minus approximately 2.5 days.

**Table 9–1: Power to demonstrate non-inferiority at 5% significance level (one-sided)**

True mean delay in healing (days)	Non-inferiority Margin	
	10%	7.5%
0	97%	85%
1	86%	57%
2	59%	24%

It is anticipated that enrolment for the study will last 18 months. During that time it is estimated that 4500 eligible patients will be seen at the centres taking part in the trial which should be an adequate number to achieve a target of 500 patients.

## 9.2 PROPOSED ANALYSES

A detailed Statistical Analysis Plan will be developed and finalised prior to database lock and the trial being unblinded. This section sets out the basic principles which will be followed for the analysis.

The response of the primary outcome variable (fracture healing at 4 weeks) in the two randomised groups will be analysed using logistic regression with adjustment for the variables used in the randomisation algorithm (study site, gender, fracture status) and other variables known to influence fracture outcome (including age, the presence of comminution and ulnar variance at presentation on X-ray). The results will be presented as an adjusted odds ratio with the corresponding 95% confidence interval and p-value. In addition a simple unadjusted comparison of the two 4 week healing rates will be made, and the result presented as a difference in healing rates along with the corresponding 95% confidence interval. The primary analysis will be conducted on an intention-to-treat basis, but given the interest in the non-inferiority comparison the per-protocol analysis will be an important secondary analysis. A similar approach will be used for other categorical outcome variables. The identification of the per-protocol population will be agreed with the Trial Steering Committee (TSC) and finalised before the data are analysed.

The analysis of the time to fracture healing will not be straightforward as there is heavy interval censoring of these data (since the 'time of healing' cannot be observed directly, and rather all that is known is whether healing has occurred by Week 2, 4, 6 or 8 (or 26)). The analysis of interval censored data is an area of active statistical research and the precise approach to be used for this analysis will be chosen nearer the end of the trial. It is likely that a parametric survival analysis will be performed, using the same covariates as for the analysis of the fracture healing rates at 4 weeks. There are libraries of statistical code available which can be used with the package "R" to perform such analyses.

Analysis of covariance will be used to compare treatment effects on continuous variables such as the DASH score, with the corresponding baseline value and the covariates identified above being included in the models. The results will be presented as adjusted mean differences along with the corresponding 95% confidence intervals and p-values.

When outcomes variables are measured on several study visits then each visit will be analysed separately. In general in terms of interpretation the Week 4 visit will be prioritised. No formal adjustments will be made to p-values to adjust for multiplicity, but the interpretation of the p-values resulting from secondary analyses will be interpreted very conservatively.

Every effort will be made to minimise missing data, especially for the key outcome measures. If more than 5% of values are missing then the primary analysis will use imputation and a complete cases analysis will be performed as a sensitivity analysis.

There is no intention to perform any formal interim analyses of the efficacy measures which might lead to a recommendation to stop the trial early on the basis of evidence of efficacy or futility. The only grounds on which the Data Monitoring Committee (DMC) could potentially recommend stopping the trial prematurely would be on the basis of a safety issue.

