#### Active range of movement

Active range of movement (AROM) will be measured at the wrist and distal radial-ulnar joints using a standard goniometer. The recording will be made in triplicate. The AROM of both the affected and unaffected hand will be measured.

The differences between the range of movement in each hand will be used to compare the two treatment groups.

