#### Grip strength

Grip strength will be measured using a JAMAR hand dynamometer using the guidelines for its use issued by the American Society for Surgery of the Hand. The grip strength of both the affected and unaffected hand will be measured.

The difference in grip strength between each hand will be used to compare the two treatment groups.

[figure not shown]

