### 7.2.7 Active Range of Movement

AROM will be assessed in participants' affected and unaffected wrist and distal radio-ulnar joint using a goniometer. Range of movement will be measured for flexion/extension, radial/ulnar deviation and supination/pronation. Each individual movement will be performed and measured 3 times. Guidelines for measuring AROM are available in the ISF.

AROM will be performed at **week 8 and week 26**.

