### 7.2.8 Grip Strength

Grip strength will be measured using a JAMAR hand dynamometer in both the affected and unaffected hand. Grip strength will be performed and measured 3 times at each required time point. Guidelines for measuring grip strength are available in the ISF.

Grip strength will be performed at **week 8 and week 26**.

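### Grip strength and range of movement have no baseline value for the planned ANCOVA, and the raw between-hand difference is generally less precise than adjusting for the unaffected hand

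*Protocol*

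**What the plan says.** Section 9.2 gives one rule for continuous outcomes: "Analysis of covariance will be used to compare treatment effects on continuous variables such as the DASH score". DASH is the only outcome named, and it does have a baseline. Under that rule the analyses are to be fitted "with the corresponding baseline value and the covariates identified above being included in the models". The covariates meant are site, gender, displacement status, age, comminution and ulnar variance.

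The schedule gives grip strength and AROM no baseline. Section 7.2.8: "Grip strength will be performed at week 8 and week 26". Section 7.2.7: "AROM will be performed at week 8 and week 26". Table 7–1 marks the same two visits, and the list in Section 7.2.1 contains neither measurement.

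Section 2.2.2 defines how the arms are compared. For grip: "The difference in grip strength between each hand will be used to compare the two treatment groups". For AROM: "The differences between the range of movement in each hand will be used to compare the two treatment groups". Both hands are measured at each of these visits; for grip, Section 7.2.8 says "Grip strength will be measured using a JAMAR hand dynamometer in both the affected and unaffected hand", and Section 7.2.7 provides the same for AROM.

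**The concern.** Read together, these sections leave two secondary outcomes with a model that contains a term nobody collects, and with an analysis variable that uses the other hand in a fixed way. Subtracting the unaffected hand is the same as adjusting for it with a coefficient set to 1. If the true slope of affected on unaffected hand is not 1, the subtraction adds noise that an estimated coefficient would avoid.

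Two things are at stake. First, Section 9.2 does not say what replaces the baseline term, so several models remain open: the raw difference, the affected hand alone, or the affected hand adjusted for the other. Second, confidence intervals for these outcomes may be wider than the same measurements allow.

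**Working it through.** **1. Fit between the rule and the schedule.** The rule needs a baseline value. Sections 7.2.1, 7.2.7 and 7.2.8 and Table 7–1 supply none for grip or AROM. The between-hand difference is not available at baseline either, so using it as the outcome does not provide the missing term. Section 9.2 also says "In general in terms of interpretation the Week 4 visit will be prioritised", and neither outcome is measured at week 4. The general rules of Section 9.2 therefore give little guidance for these two outcomes.

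**2. Inputs.** From Section 9.1: 250 per arm. The protocol gives no SD, between-hand correlation or power for grip or AROM, so there is no planned figure to reproduce. Two quantities are assumed and varied:
- r, the correlation between hands. The relevant r is the one left after the other covariates, which include gender and age.
- k, the SD of the unaffected hand divided by the SD of the affected hand.

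**3. Formulas**, in units of the affected-hand variance:
- affected hand alone: 1
- raw difference: 1 + k² − 2rk
- ANCOVA on the unaffected hand: 1 − r²

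Raw difference minus ANCOVA is k² − 2rk + r² = (k − r)². This is never negative, and it is zero only when k = r, that is, when the slope r/k equals 1. With k = 1 the variance ratio is (1 − r²) / [2(1 − r)] = (1 + r)/2.

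**4. Results with equal SDs (k = 1).** Interval width scales with the square root of the variance ratio. The detectable difference at 90% power, two-sided 5%, is (1.96 + 1.2816) × √(2/250) × √variance = 0.290 × √variance, in SDs of the affected hand.

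| r | Variance ratio | Variance reduction | Width reduction | Detectable difference: raw difference | Detectable difference: ANCOVA |
|---|---|---|---|---|---|
| 0.3 | 0.65 | 35% | 19% | 0.343 | 0.277 |
| 0.5 | 0.75 | 25% | 13% | 0.290 | 0.251 |
| 0.7 | 0.85 | 15% | 8% | 0.225 | 0.207 |
| 0.8 | 0.90 | 10% | 5% | 0.183 | 0.174 |
| 0.9 | 0.95 | 5% | 2.5% | 0.130 | 0.126 |

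Below r = 0.5 the raw difference is noisier than ignoring the unaffected hand: at r = 0.3 its variance is 2 × (1 − 0.3) = 1.40.

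**5. Unequal SDs**, r from 0.3 to 0.9. With k = 1.2 the variance ratio lies between 0.53 and 0.69. With k = 0.8 it lies between 0.78 and 1.00, reaching 1.00 at r = 0.8, where the slope is 1 and there is nothing to gain.

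**6. Bias.** Let the true effect on the affected hand be τ, and suppose treatment shifts the unaffected hand by δ. The raw difference then estimates τ − δ, and ANCOVA with slope b estimates τ − bδ. With τ = 0.20 SD and δ = 0.10 SD, the raw difference gives 0.10. ANCOVA gives 0.20 − 0.5 × 0.10 = 0.15 at b = 0.5, and 0.12 at b = 0.8.

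**7. Simulation** (3,000 trials per setting, 250 per arm, k = 1). With δ = 0 both methods recovered 0.20. Standard errors were 0.091 (raw difference) against 0.079 (ANCOVA) at r = 0.5, and 0.058 against 0.056 at r = 0.8. With δ = 0.10 the raw difference averaged 0.103 and 0.099, and ANCOVA 0.152 and 0.119, at r = 0.5 and 0.8.

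**The case against.** The strongest reply is that the sections can be combined. Section 2.2.2 fixes the outcome variable and Section 9.2 the model family, so one fits ANCOVA to the between-hand difference with the remaining covariates and drops the baseline term. Section 9.2 claims only to set out principles, names only DASH, and defers detail to a later analysis plan. This stands in part. A reader might infer that the two outcomes cannot be analysed as planned, and the protocol does not support that. What remains is that a stated term does not exist and its replacement is not named.

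A reader might also infer that the difference score is wrong. It is not. It is the specified endpoint, it reads directly as a deficit against the patient's own other hand, and under randomisation it is unbiased if the drug leaves that hand unchanged. The case against it concerns precision only, and the size rests on r and k, which the protocol does not give.

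Finally, the proposed covariate is not a baseline value. It is measured at weeks 8 and 26, during or after a systemic treatment, so the remedy is not free of assumptions. That objection stands, but it does not favour the raw difference, which needs the same assumption and is more biased when it fails and the slope lies between 0 and 1.

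**Conclusion.** The point holds as a modest and inexpensive improvement to two secondary analyses. Section 9.2 calls for a baseline covariate that the schedule does not collect for grip strength or AROM, and the planned difference is generally less precise than an analysis of the same data with an estimated coefficient.

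With equal SDs the gain runs from 35% of variance (19% of interval width) at r = 0.3 to 5% (2.5%) at r = 0.9. It is nil if the true slope is 1. It would be too strong to say that the difference always gives materially wider intervals.

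The conclusion rests on assumed r and k, and on treatment not changing the unaffected hand. Nothing here bears on week 4 healing or on the 250 per arm.

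**What to change.** For grip strength and for each AROM movement, state in Sections 2.2.2 and 9.2 that the affected-hand value (mean of the three readings) at weeks 8 and 26 will be analysed by ANCOVA. The same-visit unaffected-hand value takes the place of the missing baseline term, and the other listed covariates stay in the model. Continue to report the between-hand difference by arm.

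State the assumption that treatment does not change the unaffected hand. Add a sensitivity analysis of the affected hand alone with the other covariates, which does not need that assumption.

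If the sponsor prefers to keep the difference as the named outcome, adding the unaffected-hand value as a covariate gives the same treatment estimate and interval: subtracting that hand from the outcome changes only its own coefficient, by 1.

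The cost is small. No new measurements or patients are needed, and one degree of freedom is used. The wording of two secondary endpoints changes, which as a protocol amendment follows the approval route in Section 14.1. It should be settled before database lock and unblinding, the point by which Section 9.2 requires the analysis plan to be final.

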### 7.2.5 DASH Questionnaire

The DASH Outcome Measure is a 30-item, self-report questionnaire designed to measure physical function and symptoms in patients with any or several musculoskeletal disorders of the upper limb.

Participants will be asked to complete the DASH at **baseline, weeks 2, 4, 6, 8 and 26**. Study staff will check to ensure that all questions have been answered prior to the participant leaving the study visit.

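### DASH, pain and the other repeated continuous outcomes get a separate ANCOVA at each visit, which leaves a participant's other post-fracture scores unused when a visit is missing

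*Protocol*

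**What the plan says.** Section 9.2 names the method for continuous outcomes: "Analysis of covariance will be used to compare treatment effects on continuous variables such as the DASH score", with the baseline value and the listed covariates in the model. It then fixes how visits are handled: "When outcomes variables are measured on several study visits then each visit will be analysed separately". On emphasis it adds: "In general in terms of interpretation the Week 4 visit will be prioritised".

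The missing-data rule in the same section reads: "If more than 5% of values are missing then the primary analysis will use imputation", with complete cases as a sensitivity analysis. The phrase about the primary analysis appears earlier in 9.2, in the paragraph on week-4 healing: "The primary analysis will be conducted on an intention-to-treat basis".

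On timing, section 7.2.5 says: "Participants will be asked to complete the DASH at baseline, weeks 2, 4, 6, 8 and 26". NRS pain follows the same visits (7.2.3). Grip strength and active range of movement are measured at weeks 8 and 26 only, with no baseline (7.2.7, 7.2.8, Table 7-1). The baseline DASH and pain scores describe the participant before the fracture (7.2.1).

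**The concern.** The week-26 ANCOVA for DASH uses only participants with a week-26 score. Someone with scores at weeks 2, 4, 6 and 8 but none at week 26 contributes nothing to it, although those scores are likely to be the best available predictors of the missing one. The baseline covariate helps little, because it records recalled function before the injury and not recovery after it.

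Two things are at stake. One is precision, because recorded information goes unused. The other is bias, if the reason for a missed visit is tied to recovery in one arm and not, or not in the same way, in the other. The visit-by-visit method is stated in the protocol, so this is not a gap left for the statistical analysis plan to fill.

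**Working it through.** **Inputs.** From section 9.1: 250 per arm. The protocol states no power for these outcomes, so there is no figure of its own to reproduce. Its power for week-4 healing (at least 90%) does reproduce, with a minimum of 92.1% over control rates, but has no bearing here. Assumed: share missing at a visit m = 5 to 20%; squared multiple correlation of a visit with the participant's other post-fracture visits R² = 0.25 to 0.64; DASH SD 20; correlation ρ between week 8 and week 26 of 0.6 to 0.8.

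**Precision.** For n per arm, separate analysis uses n(1 − m). A joint likelihood model multiplies the variance by (1 − mR²), so its effective size is n(1 − m)/(1 − mR²). Take a difference with 90% power at 250 per arm: (1.960 + 1.282) × √(2/250) = 0.290 SD. Power at size n is then Φ(0.290 × √(n/2) − 1.960).

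| Missing | Separate: n per arm, power | Joint: effective n per arm, power | Gain (points) |
|---|---|---|---|
| 5% | 237.5, 88.5% | 240.5–245.4, 88.9–89.5% | 0.4–1.0 |
| 10% | 225, 86.8% | 230.8–240.4, 87.6–88.9% | 0.8–2.1 |
| 20% | 200, 82.6% | 210.5–229.4, 84.5–87.4% | 1.9–4.8 |

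For example, at 20% missing and R² = 0.64: 200/(1 − 0.128) = 229.4.

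**Bias.** Suppose the log-odds of missing week 26 change by b = 0.4 per SD of week-8 DASH in one arm only. Among those still seen in that arm, the mean week-8 score shifts by about b × m SDs, and the week-26 mean by about ρ × b × m × SD:

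- 10% missing: 0.6 × 0.4 × 0.10 × 20 = 0.48, or 0.64 with ρ = 0.8.
- 20% missing: 0.96, or 1.28 with ρ = 0.8.
- Opposite directions in the two arms: double, so 0.96–1.28 and 1.92–2.56.
- Same direction in both arms: the shifts cancel in the contrast.

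Simulation agrees (250 per arm, true week-26 difference 5 points). With opposite directions, the separate-visit estimate averaged 3.6 to 4.1 at 10% missing and 2.3 to 3.2 at 20%, while the joint estimate stayed at 4.9 to 5.2. With one arm only, the separate-visit bias was about 0.4 to 1.3 points over the same range. With the same direction in both arms it was at most 0.06 points.

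A further simulation had no true effect, correlation 0.7, about 10% missing at week 8, and a slope of 1.0 per SD of the week-6 score in one arm. Separate analysis gave −0.062 SD and the likelihood estimate −0.001 SD.

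**Scale.** The unadjusted standard error is 20 × √(2/225) = 1.9 points at 10% missing and 20 × √(2/200) = 2.0 at 20%. One-arm bias is therefore roughly a quarter to a third of a standard error at 10% missing, and a half to two thirds at 20%.

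**The case against.** The strongest reply is that imputation is already planned above 5% missing, in a section that presents itself as basic principles with a detailed analysis plan to follow. The primary analysis there could mean the main analysis of any outcome, as opposed to its sensitivity analysis. On that reading the loss remains only at 5% missing or less, where the gain is at most about 1 power point. The wording does not exclude this. The more natural reading ties the phrase to week-4 healing, and on either reading nothing says that imputation would draw on the other visits. The ambiguity stands.

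Other parts of the defence stand outright:

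- A reader might infer that separate ANCOVA is biased whenever missingness relates to recovery. For the treatment contrast it is not; the dependence must differ by arm.
- A reader might take the opposite-directions figures as the expected bias. That mechanism is extreme, and no figure in the protocol supports 10 to 20% missing at week 26.
- A reader might explain such drop-out by gastrointestinal intolerance on one arm. Sections 5.5.4 and 6.5 and note g to Table 7-1 say that stopping study drug is not withdrawal and that follow-up continues.
- A reader might treat week 26 as the main evidence on function. The protocol says no such thing and prioritises week 4.
- The repeated-measures model is not a complete remedy. If drop-out depends on the unseen week-26 score itself, the joint estimate is also biased: 0.6 to 2.0 points in a check, against 1.5 to 3.1 for the separate analysis.

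**Conclusion.** The point holds for the continuous repeated secondary outcomes: mainly DASH and NRS pain, and to a lesser extent grip strength and movement. For these, section 9.2 fixes a method that ignores recorded post-fracture scores when a visit is missing, and it does not clearly offer imputation in its place. On the assumptions above the precision cost is small. Bias is conditional on missingness depending on recovery differently by arm.

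The documents do not support reading this as a flaw in every repeated outcome. Week-4 healing falls under the imputation rule, and healing also has a time-to-event analysis over all visits. CRPS-I is binary. Grip strength and movement have only two visits and were not simulated. Nor does the protocol say that anyone is removed from the trial; the loss is specific to a visit. The planned method is permissible for secondary outcomes. The case for change is that the alternative answers the same questions with the data already collected, at little cost.

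**What to change.** In section 9.2, replace the visit-by-visit rule for continuous outcomes with wording such as:

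> DASH, NRS pain, grip strength and active range of movement will each be analysed in one mixed model for repeated measures with visit, treatment-by-visit, baseline-by-visit where a baseline exists, the covariates listed above, and unstructured covariance. The adjusted mean difference with 95% confidence interval will be reported at each visit, with week 4 prioritised. Separate ANCOVAs at each visit will be a sensitivity analysis.

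Also state which outcomes the 5% imputation rule covers. If separate ANCOVAs are kept as the main analysis, say that imputation applies to these outcomes and draws on the other visits.

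The cost is wording and some programming, with no new data. With complete data and all covariates interacted with visit, the model reproduces the separate ANCOVAs; with covariates as main effects, differences should be small. Downsides: it assumes data are missing at random, adds model terms, gains little for the two-visit outcomes, cannot recover participants with no post-baseline visit, and leaves binary CRPS-I to be handled separately.

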### **2.2 ENDPOINTS**

#### **2.2.1 Primary Endpoint**

Primary analysis will be measured by comparing the percentage of fractures healed in each treatment group at 4 weeks.

Assessment of fracture healing for the primary endpoint will be made centrally by a blinded observer. Assessment will be performed on anterior-posterior (AP) and lateral radiographs of the wrist using standard assessment methods. Fractures will be defined as healed when the following features are present:

1. Bridging of three out of four cortices
2. Radiographic evidence of endosteal healing
3. Organised trabecular bridging

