### 7.2.2 Radiological Assessment

Evaluation of fracture healing is the primary objective in this trial. Anterior-posterior (AP) and lateral radiographs of the wrist are required at **baseline** (when fracture occurs), **weeks 2, 4, 6, 8 and 26**.

Sites are required to send radiographs to the coordinating centre for central analysis. Radiographs should be anonymised and only identified by participant trial number, initials, date of birth and date of radiograph. For guidance on sending radiographs for central analysis please refer to the Investigator Site File (ISF).

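### The primary analysis switches method at 5% missing, and at or below that level it appears to drop week-4 outcomes that neighbouring films already settle

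*Protocol*

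**What the plan says.** The primary endpoint is binary at one visit (Protocol 2.2.1): "Primary analysis will be measured by comparing the percentage of fractures healed in each treatment group at 4 weeks". Section 9.2 calls the primary analysis intention-to-treat and sets this rule for missing data: "If more than 5% of values are missing then the primary analysis will use imputation". Above that level, complete cases move to the role of sensitivity analysis. The section does not say in words what happens at 5% or below, and it does not say which values make up the percentage.

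Section 7.2.2 requires films at baseline and "weeks 2, 4, 6, 8 and 26". For the time-to-healing analysis, section 9.2 treats healing as an event reached by a visit; what is known is "whether healing has occurred by Week 2, 4, 6 or 8 (or 26"). The same section has outcomes measured at several visits analysed one visit at a time. No rule in the protocol uses the week-2 or week-6 film to settle a missing week-4 status.

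Section 9.1 claims, for 250 per arm, "at least 90% power at the 5% significance level (2-sided) to detect an absolute difference of 15% in the 4 week radiological healing rates", and adds "This holds irrespective of the actual rate in the control group".

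**The concern.** The imputation method can properly wait for the analysis plan. The switch cannot, because the protocol fixes it. Two things are unsatisfactory.

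- **The primary method depends on an observed count.** One film more or less moves the primary analysis from complete cases to imputation. Because the denominator is undefined (week-4 outcomes, covariates or all data), the trigger can be disputed once the data are in.
- **Known outcomes may be thrown away.** Under the protocol's own model, a fracture unhealed at week 6 was unhealed at week 4, and one healed at week 2 was healed at week 4. Complete-case analysis drops such participants if their week-4 film is missing, which sits poorly with intention-to-treat.

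At stake are a little precision, and some bias if missing films are related to both arm and outcome.

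**Working it through.** **Inputs.** From section 9.1: 250 per arm, two-sided 5%, a 15-point difference, and healing times with mean 42 days (undisplaced) or 48 days (displaced), SD 13. From section 9.2: the 5% threshold. Assumptions: normal healing times; both adjacent films taken in everyone who misses week 4; weeks counted either from fracture or from day 14, the latest first dose allowed in section 5.5.2.

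**1. The plan's own power.** Power = Φ((d − 1.96·SE0)/SE1), with SE0 = √(2p̄(1−p̄)/n) and SE1 = √((p1(1−p1)+p2(1−p2))/n). The worst case has rates centred on 50%, that is 42.5% v 57.5%. With n = 250, SE0 = 0.04472, SE1 = 0.04421 and power = Φ(1.410) = 92.1%. The stated figure of at least 90% reproduces.

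**2. Where the switch falls.** 0.05 × 500 = 25. With 25 missing (5.0%) the implied primary is complete cases; with 26 (5.2%) it is imputation.

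**3. Power in the lower branch.** At exactly 5% missing, n = 237.5 per arm, SE0 = 0.04588, SE1 = 0.04536 and power = Φ(1.324) = 90.7%. The most that the branch costs is 92.1 − 90.7 = 1.4 points on these rounded figures (1.3 unrounded).

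**4. Share of missing week-4 outcomes fixed by adjacent films.** Share = P(T ≤ week 2) + P(T > week 6).

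| Weeks counted from | Mean (days) | P(T ≤ week 2) | P(T > week 6) | Share | Of 25 missing | Healed at week 4 |
|---|---|---|---|---|---|---|
| Fracture | 42 | 0.016 | 0.500 | 52% | 13 | 14% |
| Fracture | 48 | 0.004 | 0.678 | 68% | 17 | 6% |
| Day 14 | 42 | 0.141 | 0.141 | 28% | 7 | 50% |
| Day 14 | 48 | 0.062 | 0.269 | 33% | 8 | 32% |

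Lognormal healing times counted from fracture give 44% and 64% in place of 52% and 68%.

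**5. Gain from recovery, keeping assumptions together.** Each share implies the week-4 healing rate in the last column, so power should be computed at that rate and not always near 50%. Effective n per arm is 250 − 12.5 × (1 − share). Power for a 15-point rise from the implied rate, at 5% missing:

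| Scenario | Complete cases | Settled outcomes recovered |
|---|---|---|
| Day 14, mean 42 | 91.4% | 91.7% |
| Day 14, mean 48 | 91.9% | 92.3% |
| Fracture, mean 42 | 98.0% | 98.2% |
| Fracture, mean 48 | 99.8% | 99.8% |

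The gain is about 0.4 points or less. At the worst-case rates, the 28% share (n = 241) takes power from 90.7% to 91.1%.

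**6. Bias.** Suppose all 25 missing are in one arm and all were unhealed. Complete cases then report p × 250/225 instead of p, an excess of 1.1 points at p = 10%, 1.7 at 15% and 5.6 at 50%. With the same 25 split 12 and 13, the between-arm bias is 0.04 to 0.22 points over those rates, which is close to nothing.

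**7. Why the remainder must be imputed.** If weeks run from fracture, 97% to 99% of the settled outcomes are *not healed*; from day 14, 50% to 81% are. Filling these in and dropping the rest would generally pull the healing rate down.

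**The case against.** The best defence is that the discarding is inferred. Section 9.2 says what happens above 5% and is silent below. It describes itself as basic principles ahead of a detailed analysis plan, and nothing in it forbids deriving week-4 status from other films. Analysing visits separately concerns the models, not how status is ascertained. If the analysis plan derives the status, the value is not missing. This stands in part: the lower branch is implied, though it is the only natural reading when complete cases are named as the sensitivity analysis only above the threshold. The switch and its undefined denominator are in the protocol either way.

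It is also fair that the trigger is a missingness fraction fixed in advance and not an effect estimate, and that no inflation of type I error has been shown. That stands.

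The shares in the working are upper bounds. Someone who withdraws before week 4 has no week-6 film, and counted from fracture almost all recovery comes from that film.

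A reader might infer that the rule endangers the stated 90% power, for instance by taking complete cases at 10% missing. The documents do not support that: at 10% missing imputation is already primary, and within the complete-case branch power does not fall below 90.7%. Nor can the larger recovery shares be paired with rates near 50%, since they imply only 14% or 6% healed at week 4.

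**Conclusion.** The point holds as a small, cheap improvement. The protocol fixes a primary method that turns on 25 versus 26 missing of 500, with the counted values undefined. The implied lower branch drops some participants whose week-4 status other scheduled films determine. No stated figure is wrong, and the power claim is not at risk.

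The size is a gain of about 0.4 points of power or less at 5% missing. Bias is close to nil when missingness is balanced and matters only when it differs by arm and outcome. The recoverable share, 28% to 33% from day 14 or 52% to 68% from fracture, rests on normal healing times, the chosen time origin and both adjacent films being available. The whole argument assumes that healing, once read, is not reversed. The protocol's own time-to-healing analysis treats healing that way, but the protocol does not state it for the central reading.

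**What to change.** Replace the 5% switch with one rule that applies whatever the amount missing:

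- Set a missing week-4 status to *not healed* if a later film is unhealed, and to *healed* if an earlier film is healed.
- Multiply impute the remaining missing week-4 outcomes from treatment, the covariates of the primary model and healing status at the other visits.
- Keep complete cases as the sensitivity analysis.

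The cost is about two sentences before unblinding and a little programming; no extra films or visits are needed. The downside is the assumption that a fracture read as healed is not later read as unhealed. The rule should state it openly.
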